5.3.4.4 Dose-Limiting toxicity

The number of subjects who experience any DLT during Cycle 1 (ie, within 21 days after last dose in Cycle 1 and prior to start of Cycle 2) will be presented based on all DLT-evaluable subjects (MTD population).

5.3.4.5 Death

All deaths that occur within 30 days of last dose of study medication as well as cause of death will be listed using the Safety population.

5.3.4.6 Performance Status, Physical Exams, Vital Signs, ECG and Laboratory Evaluations

5.3.4.6.1 Laboratory Evaluation

Laboratory results will be classified according to NCI-CTCAE grade. Laboratory results not corresponding to an NCI-CTCAE term will not be graded. Laboratory toxicity shifts from baseline to worst grade will be provided. The last measurement before study medication will serve as the baseline measurement. Results for variables that are not part of the NCI-CTCAE will be presented in the listings as below, within, or above the normal limits of the local laboratory.

5.3.4.6.2 ECOG Performance status, Physical Exams and ECG

The results from physical examination, ECOG performance status and ECG will be tabulated.

The frequency of physical examination abnormalities will be summarized by scheduled time point.

ECOG performance status will be presented in a shift table.

Additionally, the frequency of abnormal ECG parameters will be tabulated by scheduled time point.

5.3.4.6.3 Vital signs

Vital sign measurements will be summarized using the following categories:

IMC-CS4 (LY3022855)

Version 2.0

- Body Temperature (C): <36 , $36\text{-}38.5$, ≥ 38.5
- Systolic Blood Pressure (mmHg): <140 , $140\text{-}160$, ≥ 160
- Diastolic Blood Pressure (mmHg): <90 , $90\text{-}100$, ≥ 100
- Arterial Pulse (beats/min): <60 , $60\text{-}120$, ≥ 120
- Respiratory Rate (breaths/min): <20 , $20\text{-}30$, ≥ 30

Vital signs will be obtained weekly during the Treatment period. At every visit that includes administration of study medication, vital signs to be checked and recorded prior to each infusion of IMC-CS4, midway through each infusion, at the end of each infusion, and every 15 minutes for the first hour following each infusion

Pre-infusion and post-infusion measurements at each visit will be presented as shift tables from:

- Preinfusion to Highest-on-Infusion
- Preinfusion to Lowest-on-Infusion
- Preinfusion to End-of-Infusion

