9.1.2 IMC-CS4 Infusion-Related Reactions

Symptoms occurring during or following infusion of investigational therapy will be defined according to the NCI-CTCAE, Version 4.0 definition of infusion-related reaction (General Disorders and Administration Site Conditions) or as allergic reaction, anaphylaxis, or cytokine release syndrome (under “Immune System Disorders” in NCI-CTCAE, Version 4.0) as detailed in [Table 11](#).

In the setting of symptoms occurring during or following infusion of investigational therapy, investigators are encouraged to use the AE term “infusion-related reaction” and any additional terms (including those not listed here) that best describe the event. Those described above should be graded as follows:

Table 11. NCI-CTCAE, Version 4.0, Infusion-Related Reactions

Adverse Event	Grade				
	1	2	3	4	5
Infusion-related reaction	Mild transient reaction; infusion interruption not indicated; intervention not indicated	Therapy or infusion interruption indicated but responds promptly to symptomatic treatment (eg, antihistamines, NSAIDS, narcotics, I.V. fluids); prophylactic medications indicated for ≤ 24 hr	Prolonged (eg, not rapidly responsive to symptomatic medication and/or brief interruption of infusion); recurrence of symptoms after initial improvement; hospitalization indicated for clinical sequelae	Life-threatening consequences; urgent intervention indicated	Death
Definition: A disorder characterized by an adverse reaction to the infusion of pharmacological or biological substances.					
Allergic reaction	Transient flushing or rash, drug fever $<38^{\circ}\text{C}$ ($<100.4^{\circ}\text{F}$); intervention not indicated	Intervention or infusion interruption indicated; responds promptly to symptomatic treatment (eg, antihistamines, NSAIDS, narcotics); prophylactic medications indicated for ≤ 24 hr	Prolonged (eg, not rapidly responsive to symptomatic medication and/or brief interruption of infusion); recurrence of symptoms after initial improvement; hospitalization indicated for clinical sequelae (eg, renal impairment, pulmonary infiltrates)	Life-threatening consequences; urgent intervention indicated	Death
Definition: A disorder characterized by an adverse local or general response from exposure to an allergen.					
Anaphylaxis	-	-	Symptomatic bronchospasm, with or without urticaria; parenteral intervention indicated; allergy-related edema/angioedema; hypotension	Life-threatening consequences; urgent intervention indicated	Death

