6.3 Planned Safety Tables

Table Number	Table Title	Population
	Dose Exposure	
14.3.1.1	IMC-CS4 Dose Exposure in Cycle 1	DLT
14.3.1.2	IMC-CS4 Dose Exposure	Safety
14.3.2	IMC-CS4 Dose Delays and Modifications in Cycle 1	DLT
14.3.2	IMC-CS4 Dose Delays and Modifications	Safety
	Adverse events	
14.3.5	Summary of Adverse Events	Safety
14.3.6	DLTs by SOC and PT (Cycle 1)	DLT
14.3.7.1	Adverse Events by SOC and PT	Safety
14.3.7.2	Adverse Events by SOC and PT (Cycle 1)	DLT
14.3.8.1	Severe Adverse Events by SOC and PT	Safety
14.3.8.2	Severe Adverse Events by SOC and PT (Cycle 1)	DLT
14.3.9.1	Serious Adverse Events by SOC and PT	Safety
14.3.9.2	Serious Adverse Events by SOC and PT (Cycle 1)	DLT
14.3.10.1	Related Adverse Events by SOC and PT	Safety
14.3.10.2	Related Adverse Events by SOC and PT (Cycle 1)	DLT
14.3.11.1	Related Severe Adverse Events by SOC and PT	Safety
14.3.11.2	Related Severe Adverse Events by SOC and PT (Cycle 1)	DLT
14.3.12.1	Related Serious Adverse Events by SOC and PT	Safety
14.3.12.2	Related Serious Adverse Events by SOC and PT (Cycle 1)	DLT
14.3.13.1	Adverse Events Resulting in Treatment Delay or Modifications by SOC and PT	Safety
14.3.13.2	Adverse Events Resulting in Treatment Delay or Modifications by SOC and PT (Cycle 1)	DLT

14.3.14.1	Adverse Events Resulting in Treatment Discontinuation by SOC and PT	Safety
14.3.14.2	Adverse Events Resulting in Treatment Discontinuation by SOC and PT (Cycle 1)	DLT
14.3.15.1	Adverse Events Resulting in Death by SOC and PT	Safety
14.3.15.2	Adverse Events Resulting in Death by SOC and PT (Cycle 1)	DLT
14.3.16.1	Adverse Events by SOC and PT and Worst Grade	Safety
14.3.16.2	Adverse Events by SOC and PT and Worst Grade (Cycle 1)	DLT
14.3.17	Deaths	Safety
	Physical Examination, Vital Signs, Laboratory Assessments, ECG	
14.3.18	Physical Examination Abnormalities by Scheduled Time	Safety
14.3.19	ECOG Performance Status Shift Table	Safety
14.3.20.3	Vital Signs Shift from Pretreatment to End-of-Study	Safety
14.3.21.1	Vital Signs Shift from Preinfusion to Highest-on-Infusion	Safety
14.3.21.2	Vital Signs Shift from Preinfusion to Lowest-on-Infusion	Safety
14.3.21.3	Vital Signs Shift from Preinfusion to End-of-Infusion	Safety
14.3.22.1	Laboratory CTC Grade Shift from Baseline to Worst Post Baseline Grade- Tests Graded in Single Direction(Either Above or Below Normal Range)	Safety

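### The SAP's blood-pressure classes have no low class, so the planned lowest-on-infusion shift table cannot show infusion hypotension

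*SAP*

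**What the plan says.** SAP section 5.3.4.6.3 introduces its classes with the rule "Vital sign measurements will be summarized using the following categories". The list for blood pressure begins "Systolic Blood Pressure (mmHg): <140" and continues with 140-160 and ≥160. For diastolic pressure it begins "Diastolic Blood Pressure (mmHg): <90" and continues with 90-100 and ≥100. Two other signs in the list do have a low class: temperature, "Body Temperature (C): <36", and pulse, below 60 beats/min.

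The section then plans three shift tables per visit, starting from the preinfusion reading: to the highest on-infusion value, to the lowest, and to the end of infusion. The second, "Preinfusion to Lowest-on-Infusion", reappears in SAP section 6.3 as Table 14.3.21.2, "Vital Signs Shift from Preinfusion to Lowest-on-Infusion", on the Safety population.

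On the protocol side, section 7.2.1 has vital signs recorded before each infusion, midway, at the end, and every 15 minutes for the following hour. Section 9 singles out infusion-related reactions for close monitoring. Table 11 in section 9.1.2 names low blood pressure in the Grade 3 anaphylaxis criteria ("allergy-related edema/angioedema; hypotension") and again in the definition of cytokine release syndrome. Section 12.5.2 says no more about vital signs than that they will be tabulated where appropriate.

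**The concern.** A table of the lowest reading during infusion exists to show falls. For blood pressure the fall of interest is into the hypotensive range, and that range is merged with normal pressure in a single bottom class that is open downward. The cuts separate only high values, so they suit the highest-on-infusion table but not the lowest-on-infusion one.

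The safety profile is a primary objective, and the protocol treats infusion reactions as a risk to be watched closely. What is at stake is the summary display of readings taken at every infusion. A table that reports no shift could be read as evidence that no falls occurred, when it could not have shown them.

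**Working it through.** No sample size, power or error rate is involved, and the plan states no figure to reproduce. The check is to place readings into the SAP's own classes and see which cell of the shift table they reach.

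Inputs from SAP section 5.3.4.6.3:
- systolic: <140, 140-160, ≥160 mmHg
- diastolic: <90, 90-100, ≥100 mmHg

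The readings below are illustrative and do not come from the documents. A reading exactly on a shared boundary was put in the upper class; none of the examples lies on one.

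| Pressure | Preinfusion → lowest (mmHg) | Cell in the shift table |
|---|---|---|
| Systolic | 120 → 110 | <140 → <140 |
| Systolic | 120 → 85 | <140 → <140 |
| Systolic | 120 → 60 | <140 → <140 |
| Systolic | 139 → 60 | <140 → <140 |
| Systolic | 150 → 135 | 140-160 → <140 |
| Systolic | 150 → 70 | 140-160 → <140 |
| Systolic | 165 → 135 | ≥160 → <140 |
| Systolic | 165 → 70 | ≥160 → <140 |
| Diastolic | 75 → 70 | <90 → <90 |
| Diastolic | 75 → 40 | <90 → <90 |
| Diastolic | 95 → 85 | 90-100 → <90 |
| Diastolic | 95 → 40 | 90-100 → <90 |

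Two results follow.

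1. **Start below 140/90.** The subject is already in the bottom class for both pressures. There is nowhere lower to go, so every fall, of any size, is tabulated as no shift. A systolic fall of 120 − 110 = 10 mmHg and one of 120 − 60 = 60 mmHg are indistinguishable.
2. **Start at or above 140 or 90.** A downward shift can appear, but it does not say how far the pressure fell. A systolic fall of 150 − 135 = 15 mmHg to an ordinary value shares its cell with a fall of 150 − 70 = 80 mmHg.

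Each pressure has three cells that end in the bottom class, one per starting class, and none separates a normal lowest reading from a hypotensive one. The end-of-infusion table (14.3.21.3) uses the same classes and has the same limit.

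The wording also leaves boundary readings with two possible classes: 38.5 °C, 160 mmHg, 100 mmHg, 120 beats/min and 30 breaths/min each fall in both a middle and a top class. This affects only readings exactly on the boundary and has no bearing on hypotension.

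**The case against.** **Hypotension has other routes into the report.** Protocol section 8.1 requires reporting of clinically significant vital-sign findings that lead to a diagnosis. Infusion reactions, anaphylaxis and cytokine release are graded adverse events, and SAP sections 5.3.4.3 and 6.3 tabulate adverse events by term, grade, relationship and effect on treatment. SAP section 6.4 lists individual vital signs in Listing 20. This stands, and it limits the point to the summary table. A reader might infer that infusion hypotension would vanish from the report; the documents do not support that. What remains is a fall that is not recorded as an adverse event, which would be visible only as raw listing values.

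**A general rule might fill the gap.** SAP section 5.2.3 summarises continuous variables with, among other statistics, the minimum, which would expose a low reading. But section 5.3.4.6.3 is the specific rule for vital signs and prescribes classes, and section 6.3 plans only shift tables for them. The general rule does not cure the problem.

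**The SAP does not say outright that the shift tables use these classes.** True, and SAP section 6 leaves the final table list to a separate shell document that is not available here. But a shift table needs classes, and these are the only ones given.

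**The 38.5 °C temperature cut.** A reader might infer a conflict with the 38.0 °C in the DLT definition (protocol section 4.1.4). There is none: that figure applies to fever complicating Grade 3 or 4 neutropenia and is not a general fever definition that a display class must match.

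**Decision impact.** The analyses are descriptive (protocol section 12.1). Escalation rests on DLTs and safety review meetings (sections 4.1.1 and 12.8), not on this table. That also stands.

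**Conclusion.** The point holds for the planned summary of on-infusion blood pressure. With the classes as written, Table 14.3.21.2 cannot show infusion hypotension. For subjects starting below 140/90 this covers all falls, by construction; for subjects starting higher, the table records a drop in class without showing whether it ended at a normal or a hypotensive value. The documents do not say how many subjects will start below 140/90, so the number of falls affected cannot be given.

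The conclusion assumes that the shift tables use the only classes the SAP provides, and that the shell document does not add a lower one. It does not extend to the adverse-event tables or Listing 20, to the dose-escalation decisions, or to the recommended Phase 2 dose. It is a reporting defect that should be corrected because a stated rule defeats the purpose of a safety display the SAP itself plans.

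**What to change.** In SAP section 5.3.4.6.3, do one or both of the following:
- Add a low class for systolic and for diastolic pressure, with cuts that the sponsor pre-specifies. Neither document gives a hypotension threshold, so the SAP should describe the cuts as display assumptions.
- Summarise the change from the preinfusion reading to the lowest on-infusion value as a continuous variable, which needs no threshold.

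In the same edit, make every class boundary non-overlapping, so that each reading belongs to one class only. Carry the change into the shells for Tables 14.3.21.2 and 14.3.21.3. Leave the temperature cut as it is.

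The readings are already collected under protocol section 7.2.1, so the cost is SAP wording and table shells. No visit, measurement, escalation rule or sample size changes.

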5.3.5 Other Assessments or Analyses

5.3.5.1 Pharmacokinetic Assessments

Blood samples for PK will be analyzed by the ImClone Department of Clinical Pharmacology. Parameters to be reported may include, but not be limited to, C_{\max} , C_{\min} , AUC, $t_{1/2}$, Cl, and V_{ss} of IMC-CS4, and will be generated using a noncompartmental model. PK parameters will be summarized using descriptive statistics.

5.3.5.2 Pharmacodynamic Assessments

Tissue (DNA, RNA and protein analyses) and whole blood analyses, including analyses of circulating levels of CSF-1, will be descriptive, and correlations to safety and/or

efficacy will be performed as appropriate. There will be a separate SAP describing the analysis of pharmacodynamic assessments.

5.4 Interim analyses and data monitoring committees

For more details about safety reviews and monitoring committees please refer to Section 12.6.28 of the protocol.

5.5 Changes in planned analyses from the protocol

None

6 Planned summary tables and Listings

Planned table numbering and title may be modified for the clinical study report (CSR), with the final list to be reflected in a separate table shell document.

6.1 Planned Demographic Tables

Table Number	Table Title	Population
14.1.1	Patient Disposition	All enrolled patients
14.1.2	Demographic and Baseline Characteristics	Safety
14.1.3	Pre-Treatment Disease Characteristics	Safety
14.1.4	Sites of Metastatic Disease at Screening	Safety
14.1.5	Prior Anti-Cancer Therapy or Surgery	Safety
14.1.6	Medical History	Safety

6.2 Planned Efficacy Tables

Table Number	Table Title	Population
14.2.1	Best Overall Response, Disease Control Rate and Response Rate	Safety

6.3 Planned Safety Tables

Table Number	Table Title	Population
	Dose Exposure	
14.3.1.1	IMC-CS4 Dose Exposure in Cycle 1	DLT
14.3.1.2	IMC-CS4 Dose Exposure	Safety
14.3.2	IMC-CS4 Dose Delays and Modifications in Cycle 1	DLT
14.3.2	IMC-CS4 Dose Delays and Modifications	Safety
	Adverse events	
14.3.5	Summary of Adverse Events	Safety
14.3.6	DLTs by SOC and PT (Cycle 1)	DLT
14.3.7.1	Adverse Events by SOC and PT	Safety
14.3.7.2	Adverse Events by SOC and PT (Cycle 1)	DLT
14.3.8.1	Severe Adverse Events by SOC and PT	Safety
14.3.8.2	Severe Adverse Events by SOC and PT (Cycle 1)	DLT
14.3.9.1	Serious Adverse Events by SOC and PT	Safety
14.3.9.2	Serious Adverse Events by SOC and PT (Cycle 1)	DLT
14.3.10.1	Related Adverse Events by SOC and PT	Safety
14.3.10.2	Related Adverse Events by SOC and PT (Cycle 1)	DLT
14.3.11.1	Related Severe Adverse Events by SOC and PT	Safety
14.3.11.2	Related Severe Adverse Events by SOC and PT (Cycle 1)	DLT
14.3.12.1	Related Serious Adverse Events by SOC and PT	Safety
14.3.12.2	Related Serious Adverse Events by SOC and PT (Cycle 1)	DLT
14.3.13.1	Adverse Events Resulting in Treatment Delay or Modifications by SOC and PT	Safety
14.3.13.2	Adverse Events Resulting in Treatment Delay or Modifications by SOC and PT (Cycle 1)	DLT

14.3.14.1	Adverse Events Resulting in Treatment Discontinuation by SOC and PT	Safety
14.3.14.2	Adverse Events Resulting in Treatment Discontinuation by SOC and PT (Cycle 1)	DLT
14.3.15.1	Adverse Events Resulting in Death by SOC and PT	Safety
14.3.15.2	Adverse Events Resulting in Death by SOC and PT (Cycle 1)	DLT
14.3.16.1	Adverse Events by SOC and PT and Worst Grade	Safety
14.3.16.2	Adverse Events by SOC and PT and Worst Grade (Cycle 1)	DLT
14.3.17	Deaths	Safety
	Physical Examination, Vital Signs, Laboratory Assessments, ECG	
14.3.18	Physical Examination Abnormalities by Scheduled Time	Safety
14.3.19	ECOG Performance Status Shift Table	Safety
14.3.20.3	Vital Signs Shift from Pretreatment to End-of-Study	Safety
14.3.21.1	Vital Signs Shift from Preinfusion to Highest-on-Infusion	Safety
14.3.21.2	Vital Signs Shift from Preinfusion to Lowest-on-Infusion	Safety
14.3.21.3	Vital Signs Shift from Preinfusion to End-of-Infusion	Safety
14.3.22.1	Laboratory CTC Grade Shift from Baseline to Worst Post Baseline Grade- Tests Graded in Single Direction(Either Above or Below Normal Range)	Safety
14.3.22.2	Laboratory CTC Grade Shift from Baseline to Worst Post Baseline Grade- Tests Graded in Single Direction(Either Above or Below Normal Range)	Safety
14.3.22.3	Laboratory CTC Grade Shift from Baseline to Worst Low Post Baseline Grade -Tests Graded in Both Directions (Above and Below Normal Range)	Safety
14.3.23	Laboratory CTC Grade Shift Shift from Pretreatment to End-of-Study	Safety
14.3.24	Electrocardiogram	Safety
14.3.25	Pharmacodynamic Biomarkers	Safety
14.3.26	IMC-CS4 Antibodies	Safety

6.4 Planned Patient Data Listings

Listing Number	Listing Title	Population
	Baseline Characteristics	
1	Patient Disposition	All enrolled patients
2.1	Definition of In- and Exclusion Criteria	NA
2.2	Inclusion Criteria	All enrolled patients
2.3	Exclusion Criteria	All enrolled patients
2.4	Exemption of In- and Exclusion Criteria	All enrolled patients
3	Protocol Deviations	Safety
4	Demographic and Baseline Characteristics	Safety
5	Pre-Treatment Disease Characteristics	Safety
6	TNM Staging	Safety
7	Site of Metastatic Disease at Screening	Safety
8	Previous Anti-Cancer Therapy	Safety
9	Prior Disease Related Radiotherapy	Safety
10	Prior Disease-Related Surgery	Safety
11	Medical History	Safety
12	Pregnancy Test	Safety
	Efficacy	
13.1	Tumor Measurements – Target Lesions	Safety
13.2	Tumor Measurements – Non-Target Lesions	Safety
13.3	Tumor Measurements – New Lesions	Safety
13.4	Tumor Measurements – Comments	Safety
13.5	Best Overall Response	Safety
13.6	Radiographic Scans	Safety
	Dose Exposure	
14.1	IMC-CS4 Administration	Safety
14.2	IMC-CS4 Modifications	Safety
14.3	IMC-CS4 Infusion Interruptions	Safety

14.4	IMC-CS4 Dose intensity	Safety
	Adverse Events	
15.1	Dose-Limiting Toxicities	DLT
15.2	Adverse Events	Safety
15.3	Serious Adverse Events	Safety
15.4	Adverse Events Resulting in IMC-CS4 Modifications	Safety
15.5	Adverse Events Resulting in IMC-CS4 Treatment Discontinuation	Safety
15.6	Adverse Events Resulting in Death	Safety
15.7	Adverse Event Comments	Safety
16.1	Concurrent Therapy and Procedures for the Treatment of AEs	Safety
16.2	Concurrent Therapies and Procedures not for the Treatment of AEs	Safety
17	Death Reports	Safety
	Physical Examination, Vital Signs, Laboratory Assessments	
18	Weight, Height and ECOG Performance Status	Safety
19	Physical Examination	Safety
20	Vital Signs	Safety
21.1	Laboratory Reference Ranges	NA
21.2	Listing of Patients With \geq Grade 3 Abnormal Laboratory Results	Safety
22	Laboratory - Hematology	Safety
23	Laboratory - Coagulation	Safety
24	Laboratory - Serum Chemistry	Safety
25	Laboratory - Urinanalysis	Safety
26	Electrocardiogram	Safety
27	Hospitalization	Safety
28	Pharmacodynamic Biomarkers	Safety
29	IMC-CS4 Antibodies	Safety

Appendix 1: List of Abbreviations

AE	adverse event
BOR	best overall response
CR	complete response
CRO	contract research organization
CSF-1	colony-stimulating factor-1
CSF-1R	colony-stimulating factor-1 receptor
CSR	Clinical study report
DLT	dose-limiting toxicity
ECG	electrocardiogram
ECOG	Eastern Cooperative Oncology Group
eCRF	electronic case report form
FPV	first patient visit
MedDRA®	Medical Dictionary for Regulatory Activities
MTD	maximum tolerated dose
NCI-CTCAE	National Cancer Institute Common Terminology Criteria for Adverse Events
NE	non-evaluable
PD	progressive disease
PK	pharmacokinetic(s)
PR	partial response
PT	preferred term
RECIST 1.1	Response Evaluation Criteria in Solid Tumors, Version 1.1
SAE	serious adverse event
SAP	Statistical Analysis Plan
SD	stable disease
SOC	system organ class
TNM	tumor, nodes, and metastases
WHOdrug	world health organization drug information

